10. STATISTICAL DESIGN AND ANALYSES

10.1 OVERVIEW OF STUDY DESIGN

The WAVE trial is a randomized double masked placebo controlled factorial clinical trial. The trial will randomize women to active or placebo HRT (estrogen or, when appropriate, estrogen with progesterone), and to active or placebo vitamin combination (1000mg/day of vitamin C and 800 IU/day of vitamin E). The trial will be conducted at five participating clinical centers and will randomize a total of 450 postmenopausal women with angiographically documented coronary artery disease. The primary objective of the WAVE trial is to determine whether hormone replacement or antioxidant therapy favorably affect coronary atherogenesis during approximately a three year study interval. Response to the treatments will be assessed by the mean, for each woman, of the changes in minimum lesion diameter (MLD), of study defined lesions, as estimated at baseline and at the exit angiogram, between the randomized treatment groups. Two null hypotheses will be tested in this trial:

1. There is no difference in average change in mean lesion diameter per year between women who receive hormone replacement therapy and women who receive placebo.
2. There is no difference in average change in mean lesion diameter per year between women who receive antioxidants and women who receive placebo.

Although both hypotheses will be tested, no adjustment will be made for multiple comparisons because the trial is powered to test both hypotheses at the 0.05 level.

10.2 PRIMARY ENDPOINT

10.2.1 Definition of the Primary Endpoint

The primary endpoint will be evaluated in all segments containing 15 - 75% lesions noted on the entry angiogram or any new lesions \geq 15% observed on a follow-up angiogram

within the study duration. These segments are referred to as the study endpoint segments. The change in MLD of each segment is divided by the time between the entry arteriogram and the final angiogram within the prespecified study follow-up-period. An exception will be made for intercurrent angiograms and revascularization procedures: these procedures will provide the concluding measurements for those segments that were intervened. For such segments, the change in MLD will be divided by the time between the baseline angiogram and the pre-procedure intercurrent angiogram. The study goal is to obtain a protocol angiogram within the last six months of the scheduled end of the trial. With recruitment anticipated to occur over a 12-15 month period, this implies an anticipated average follow-up of approximately 40.5 months. If the patient has had a coronary angiogram for clinical indications within six months of the planned study termination, the results from that arteriogram can be used in lieu of an exit angiogram. If the angiogram has occurred more than six months before the end of the trial an additional angiogram will be requested.

Patients eligible for entry into the study will have one or more segments containing 15 - 75% stenosis which have not been influenced by prior catheter interventions. These are referred to as qualifying segments and lesions. Segments identified on the entry as containing a 15 - 75% stenosis or on the concluding arteriogram(s) as containing any lesion $\geq 15\%$ are considered endpoint segments. This definition automatically includes those segments which originally qualified the patient for study entry. Segments included in this analysis must be in the main coronary vessels or their major branches and have a reference diameter >1.5 mm. Segments or lesions progressing to 99 - 100% stenosis are automatically assigned a MLD of 0.0 mm. Non-visualized segments distal to total occlusions are considered lost to follow-up.

The 15 - 75% lesion determination is based on the mean of the most anatomically relevant proximal and distal reference margins that can be ascertained. These reference margins may extend proximally or distally beyond the margins of the segment, if the lesion/disease is extensive. Segments may range in length from 3 to 25mm.

Intercurrent angiograms are those performed for clinical, rather than protocol indications after the entry angiogram, but prior to the scheduled exit angiogram. Intercurrent angiograms performed immediately prior to any catheter based interventions will be assessed by the Central Angiographic Laboratory to identify whether either the original qualifying segments or new segments have been subject to manipulation that would alter their subsequent natural history. Intervened segments which contain a new stenosis (i.e. $\geq 15\%$) are included as endpoint segments. However, their exposure times are adjusted in accordance with the interval between the initial angiogram and the intercurrent angiogram.

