1. OBJECTIVE

The WAVE trial is a factorial randomized double masked controlled clinical trial. The trial will randomize women to active or placebo hormone replacement therapy (estrogen and, when appropriate, estrogen with progesterone), and to active or placebo vitamin combination (1000mg/day of vitamin C and 800 IU/day of vitamin E). For each patient, the minimum lesion diameter (MLD), i.e., the minimum lumen diameter in a lesion, will be measured for all segments containing a lesion either at baseline or at follow up. The change in MLD between baseline and follow-up will then be computed for all such segments. The primary outcome for each patient is the time adjusted average of the changes in MLDs from baseline to follow- up.

The primary null hypotheses of the trial are:

- a) The average change in MLD of women receiving hormone replacement therapy will not differ significantly from that of women receiving placebo.

- b) The average change in MLD of women receiving antioxidant therapy will not differ significantly from that of women receiving placebo.

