3.2 INCLUSION CRITERIA

To be eligible for randomization, women must:

1. Be postmenopausal by one of the following criteria:
 - a. Have had a bilateral oophorectomy at any age,
 - b. Be ≥ 55 years of age (or have an FSH ≥ 40 , if under age 55)
 - c. $<$ age 55 and FSH ≥ 40

Women under 45 years of age without a bilateral oophorectomy, or FSH ≥ 40 are excluded.

2. Have a WAVE protocol angiogram performed within four months of randomization, while hemodynamically stable, demonstrating at least one vessel segment with a 15-75 percent stenosis. The qualifying artery may not have been intervened (dilated, atherectomized or stented). If the angiogram was performed within 2 weeks of a myocardial infarction, the qualifying segment may not be the infarct segment.
3. Provide signed informed consent.

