10.3.3 Additional Analyses

- a) *Study of lesions >75%*: change in the, by patient, average of the MLD of all segments containing >75% stenosis on the entry angiogram. The change is adjusted for the actual time interval between the entry arteriogram and the follow-up arteriogram. Many of these segments may become subject to catheter based or surgical interventions during the course of the study.

- b) *Study of post PTCA restenosis*: change in the MLD of any stenosis having catheter interventions from the immediate post PTCA procedure to the exit angiogram. All lesions that were treated within 6 weeks prior to or during the entry angiographic procedure are included in this analysis. However, there must be at least a 6-month, in study, interval between the interventional procedure and the follow-up angiogram which may be either a protocol mandated, concluding angiogram or a clinically indicated intercurrent angiogram. The primary analysis for this study will be based on the one lesion per patient that shows the greatest change from initial eligibility to follow-up. A second analysis will consider each PTCA treated lesion as an individual statistical entity. Both of these analyses will include the type of catheter-based intervention along with multiple other standard angiographic lesion characteristics as covariates.

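### Section 10.2.1 defines the primary endpoint segments in two conflicting ways, and neither wording keeps out segments dilated or stented before or at entry that show 15–75% on the entry film

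*Protocol*

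**What the plan says.** The Protocol states the endpoint-segment rule in three places:

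- Section 10.2.1, first paragraph: "The primary endpoint will be evaluated in all segments containing 15 - 75% lesions noted on the entry angiogram or any new lesions" of at least 15% on a follow-up film.
- Section 10.2.1, second paragraph: "Segments identified on the entry as containing a 15 - 75% stenosis or on the concluding arteriogram(s) as containing any lesion" of at least 15%.
- Section 1: the MLD "will be measured for all segments containing a lesion either at baseline or at follow up", with no percentage limits.

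The bars on treated and infarct segments are written for eligibility. Section 10.2.1 asks that each patient have at least one of the following: "segments containing 15 - 75% stenosis which have not been influenced by prior catheter interventions. These are referred to as qualifying segments and lesions". Section 3.2 puts it by artery: "The qualifying artery may not have been intervened (dilated, atherectomized or stented"). It adds that, if the film was taken within 2 weeks of a myocardial infarction, "the qualifying segment may not be the infarct segment". The endpoint set is then made wider than the qualifying set: "This definition automatically includes those segments which originally qualified the patient for study entry". The limits stated for inclusion in the primary analysis concern the vessel and a reference diameter above 1.5 mm.

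Section 10.3.3 gives lesions above 75% at entry an analysis of their own, and another to catheter-treated lesions: "All lesions that were treated within 6 weeks prior to or during the entry angiographic procedure are included in this analysis". For procedures during the trial, Sections 10.2.1 and 10.2.2 close the segment at the film taken before the procedure.

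**The concern.** The primary endpoint is each woman's average, over her endpoint segments, of the annualised change in MLD. Which segments enter that average decides the result. With two rules in one section, the same films can yield two different primary values for the same woman. If the choice is left until films have been measured, it becomes a post hoc choice of primary outcome.

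The second issue is what the average measures. Section 10.1 aims at coronary atherogenesis. Restenosis after dilation or stenting, and early change in a recent infarct segment, are different processes. The protocol protects the endpoint from procedures during follow-up but has no matching rule, at endpoint-segment level, for procedures before or at the entry film.

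**Working it through.** **Each type of segment under each wording.**

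| Segment | 10.2.1, first paragraph | 10.2.1, second paragraph | Section 1 |
|---|---|---|---|
| Untreated, 15–75% at entry | in | in | in |
| Untreated, below 15% at entry, at least 15% at follow-up | in | in | in |
| Above 75% at entry, at least 15% on the concluding film | out (neither 15–75% nor new) | in | in |
| Dilated or stented before or at entry, 15–75% on the entry film | in | in | in |
| Dilated or stented before or at entry, outside 15–75% on the entry film, at least 15% at the end | out if above 75%; unclear if below 15% (is restenosis new?) | in | in |
| Infarct segment, film within 2 weeks of the infarction, 15–75% at entry | in | in | in |
| Infarct segment, same timing, above 75% at entry | out | in | in |

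Two results follow.

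1. The wording conflict decides rows 3, 5 and 7: mainly lesions above 75% at entry, plus treated or infarct segments outside 15–75% at entry.
2. Rows 4 and 6 do not depend on the conflict. Choosing the narrower wording would leave them in, so they need a rule of their own.

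**Is the infarct row possible?** Yes. Section 3.3 excludes an infarction less than 4 weeks before randomization, but Section 3.2 accepts a film up to four months old. A woman can have a film within 2 weeks of an infarction and be randomized later. Section 3.2 itself provides for this.

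**Why extra variance is plausible.** Section 10.3.3 expects many lesions above 75% to be treated during the study. Section 10.2.2 would then close such a segment early and divide by the shorter interval. In that section's own example, 1 mm at 6 months is 1/0.5 = 2 mm per year, and 1 mm at 3 years is 1/3 = 0.33 mm per year: a ratio of 6. If these lesions count, some may carry heavy weight. How many is not stated.

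**Can the effect on power be computed?** The sample size itself reproduces. With effect size 0.334, two-sided alpha 0.05 and power 0.90 (Section 10.4), n per arm = 2 × (1.960 + 1.282)² / 0.334² = 2 × 10.51 / 0.1116 = 188.4, so 189 per arm and 378 in total, against the stated 380. The inputs are a patient-level effect size, alpha and power. The protocol gives no number of segments per woman, no share of segments above 75% or already treated, and no variance by segment type. A power loss cannot be derived from it.

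**The case against.** The best defence is that the context favours the narrower reading. The first paragraph of Section 10.2.1 says *new*, and so does the later text on intervened segments; one sentence drops it. Section 1 is a summary. Section 10.3.3 shows that lesions above 75% and PTCA-treated lesions were to be studied apart. Section 12.2.3 gives endpoint definitions to a subcommittee, and Section 12.2.9 has one masked laboratory apply criteria set in advance. This makes the narrower reading the likelier intention and divergent readings less likely. It does not remove the contradiction: the second sentence is also written as a definition, and nothing says which prevails. Nor does it touch treated segments at 15–75%, which the narrower reading admits.

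Several stronger readings are tempting but not supported:

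- *The wider wording is what lets in dilated, stented or infarct segments.* Those at 15–75% on the entry film enter under both wordings.
- *The gain in diameter from PTCA would be counted as regression.* Sections 10.2.1 and 10.2.2 close revascularized segments at the pre-procedure film. Read literally, a segment treated just after the entry film has no later pre-procedure film from which a gain could be taken.
- *A procedural shift in a woman's average can be judged against 0.4 mm.* That threshold in Section 10.3.1 is for single segments, not for a patient's average.
- *Such segments will be common.* Section 7.1 lists post-intervention catheterizations among the screening sources but gives no frequencies.

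**Conclusion.** The point holds as a contradiction in the definition of the sole primary endpoint, together with a separate gap for segments treated before or at entry. The conflict mainly determines whether lesions above 75% at entry count. The gap exists whichever wording is chosen.

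The expected harm is ambiguity, dilution of any treatment effect and added variance. A reader might infer bias between the arms, but the documents do not show it. Procedures and infarctions before entry are baseline features that randomization should balance, and the central laboratory is masked. A reader might also expect a figure for lost power; any such figure would rest on segment counts and variances that the protocol does not give, so none is offered. The effect size of 0.334 comes from four published trials whose segment rules are not in the document, so it is also unknown whether the planned power already reflects similar segments.

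**What to change.** Use one definition in Sections 1, 10.2.1 and 10.2.2: a segment is an endpoint segment if it has 15–75% stenosis at entry, or less than 15% at entry and at least 15% at follow-up. Then state at endpoint-segment level that:

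- segments above 75% at entry are excluded from the primary endpoint and analysed only under Section 10.3.3(a);
- segments with a catheter intervention before or at the entry procedure are excluded and analysed only under Section 10.3.3(b). That analysis reaches back only 6 weeks, so say what happens to segments treated earlier;
- the existing 2-week infarct-segment bar applies to endpoint segments too, or such segments are knowingly included.

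Also reconcile Section 3.2, which bars intervention in the qualifying artery, with Section 10.2.1, which bars it in the qualifying segment.

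The cost is protocol wording and coding rules at the Central Angiographic Laboratory, which already reads all films. Some segments leave the primary average. No woman should lose her endpoint through these exclusions, because eligibility already requires an untreated 15–75% segment that is not a recent infarct segment. The change should be made before films are quantified.

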10.2.2 Primary Analysis

The change in MLD will be computed for each of the patient's study endpoint segments . The follow up angiogram is not necessarily the same for all the segments in a patient: for segments that were revascularized prior to the concluding angiogram, the MLD will be read from the angiogram before the revascularization. For segments that were not revascularized before the concluding angiogram, the MLD will be read from the concluding angiogram. Each of the changes in MLD will then be divided by the time between the entry angiogram and the follow up angiogram. For patients who have revascularization procedures prior to the concluding angiogram, the changes in MLD of various segments may thus be divided by different quantities. These changes in MLD, divided by the appropriate quantities are then averaged for the patient. This average is the primary endpoint for the patient. A segment with a 1 mm change at the time of an intercurrent angiogram at 6 months will therefore have more weight in the average than another segment with a 1 mm change after 3 years. With the time adjustment described above, the primary endpoint is basically a measure of the average rate of change in MLD in diseased segments.

The primary endpoint in the treated and control groups will be compared using a nonparametric rank test based on the Van der Waerden scores. This test, which is similar to a Wilcoxon test, was selected for two reasons. First, for the sample sizes contemplated in this study, it has essentially the same power as the usual t-test under the assumption of normality and

better power than the t-test if the data are markedly non-normal. Second, it readily accommodates patients who had an MI or died by assigning them the worst rank. It also has better power than the Wilcoxon test under the assumption of normality. The primary analysis for the study will be conducted using the “intention to treat” paradigm, with all patients retained in their original randomization group, regardless of their level of compliance with their assigned treatments.

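### Segments revascularized between the entry film and randomization can enter the primary endpoint, scored on pre-treatment change divided by days or weeks

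*Protocol*

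**What the plan says.** Protocol Section 10.2.2 builds the primary endpoint in two steps. First, "Each of the changes in MLD will then be divided by the time between the entry angiogram and the follow up angiogram". Then, "These changes in MLD, divided by the appropriate quantities are then averaged for the patient". Segments are equally weighted as rates, so a segment with a short interval pulls harder per millimetre. The section says so: "A segment with a 1 mm change at the time of an intercurrent angiogram at 6 months will therefore have more weight in the average". Its comparison is a segment measured after three years.

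Section 10.2.1 ends an intervened segment at its last film before the procedure; for such segments "the change in MLD will be divided by the time between the baseline angiogram and the pre-procedure intercurrent angiogram". It gives no lower limit for that time. It defines the films concerned as follows: "Intercurrent angiograms are those performed for clinical, rather than protocol indications after the entry angiogram, but prior to the scheduled exit angiogram". The window therefore opens at the entry film, not at randomization.

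Section 3.2, inclusion criterion 2, sets how far apart those two dates may be. A woman must "Have a WAVE protocol angiogram performed within four months of randomization". The same criterion protects one vessel: "The qualifying artery may not have been intervened (dilated, atherectomized or stented"). It says nothing about other arteries that contain endpoint segments.

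The groups are compared by a Van der Waerden rank test, with the worst rank for MI or death (Section 10.2.2).

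**The concern.** Error in reading an MLD does not shrink because two films are close together. Dividing by the interval multiplies that error by 1/time, so a segment with a very short interval can settle the woman's score almost alone. Van der Waerden scores weight extreme ranks more heavily than Wilcoxon scores do, so misplaced extremes matter.

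For a film taken after randomization, part of the change may at least reflect treatment. For a film taken between entry and randomization, none of it can. The definitions admit such a segment if it lies outside the qualifying artery and either had a 15-75% lesion at entry or shows a new lesion of at least 15% on the pre-procedure film. This is foreseeable, since Section 7.1 expects to find candidates through logs of catheterizations done before and after interventions. At stake are the precision of the primary comparison and the principle that the primary score should measure change that could occur on treatment.

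**Working it through.** **Inputs from the protocol.** Usual interval T = 40.5 months = 3.375 years (Section 10.2.1). Up to 4 months from entry film to randomization (Section 3.2). Segment change threshold 0.4 mm (Section 10.3.1 c). Effect size 0.334, power 0.90, two-sided alpha 0.05, total N = 380 (Section 10.4).

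**Assumptions.** k = 4 endpoint segments per woman, one of them closed early at time t. Reading error is equal and independent across segments. The variance shares do not depend on the size of that error.

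**The plan's own figures first.** 1 mm at 6 months is 1/0.5 = 2.00 mm/yr; 1 mm at 3 years is 1/3 = 0.33 mm/yr. The ratio is 6, in line with the text's remark. The sample size also reproduces: 2 × (1.960 + 1.282)² / 0.334² = 188.4, so 189 per arm or 378 in total (stated 380), and 380/0.85 = 447 (stated 450).

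**Dominance of one early segment.** Let w = 40.5/t, with t in months.

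- Share of the woman's noise variance: w² / (w² + k − 1).
- Noise SD relative to a woman with no early film, mean of rates: √((w² + 3)/4).
- The same ratio for total change over total time: 4T/(t + 3T).

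| t (months) | w | Variance share | SD ratio, mean of rates | SD ratio, total/total |
|---|---|---|---|---|
| 0.5 | 81 | 99.95% | 40.5 | 1.33 |
| 1 | 40.5 | 99.8% | 20.3 | 1.32 |
| 2 | 20.3 | 99.3% | 10.2 | 1.31 |
| 4 | 10.1 | 97.2% | 5.1 | 1.29 |
| 6 | 6.75 | 93.8% | 3.5 | 1.27 |
| 12 | 3.4 | 79.2% | 1.9 | 1.21 |

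For t = 6 months in units of segment noise: √((1/0.5² + 3/3.375²)/16) = 0.516, against 0.148 with no early film and √4/(0.5 + 3 × 3.375) = 0.188 for total over total. The result is not sensitive to k: at 6 months the share is 97.9% for k = 2 and 86.7% for k = 8.

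**In millimetres.** A difference of 0.2 mm, half the protocol's threshold for calling a segment changed, is 2.4 mm/yr at 1 month and adds 2.4/4 = 0.6 mm/yr to a four-segment score. The same 0.2 mm at 40.5 months adds 0.2/3.375/4 = 0.015 mm/yr. For scale, a woman whose four segments each lose 0.4 mm over 40.5 months scores 0.4/3.375 = 0.12 mm/yr. That benchmark spreads a threshold with no time base over the usual follow-up.

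**Can such a film precede randomization?** Four statements have to be read together.

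1. The intercurrent window opens after the entry film (10.2.1).
2. The entry film may be four months before randomization (3.2).
3. The bar on intervention covers the qualifying artery (3.2).
4. Section 10.2.1 refers to the study duration and to a prespecified follow-up period, but neither is said to start at randomization.

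Nothing excludes the film, so the first four rows of the table can arise from pre-treatment change.

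**Trial level, illustrative only.** A simulation used N = 380, five segments, SD of change 0.1-0.2 mm, score SD 0.05-0.10 mm/yr, and early films uniform from 0.5 to 6 or 12 months. Van der Waerden power fell from about 0.90 to 0.84-0.90 if 5% of women had one early film, 0.78-0.89 at 10%, and 0.63-0.87 at 20%. Total over total stayed at 0.88-0.92. With four segments and films spread over 6-36 months, the loss was about 1 point or less. These runs cover all early films, not only those before randomization, and contain no true extra progression in the treated segments.

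**The case against.** The strongest reply is that the weighting is deliberate. Section 10.2.2 discloses it and describes the endpoint as an average rate of change in diseased segments. An intercurrent film closes only segments that were intervened, and many of those will have truly narrowed, so their pull is not all noise.

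A reader might infer that the mean of rates is an error and that total change over total time should replace it. The documents do not support that, because the choice is a trade-off. Suppose one of four segments loses 1 mm at 6 months and the rest are stable. The planned score is 2/4 = 0.50 mm/yr; total over total gives 1/10.625 = 0.094, hardly more than the 0.074 for the same loss at 40.5 months. The alternative nearly removes the intended weighting. In a simulation where treatment worked only by preventing fast progression that leads to a procedure (12% against 24% of women, mean loss 0.8 mm), the planned score had power 0.27-0.40 and the alternative 0.12-0.24. With equal 20% procedure rates and true loss, the alternative was better (0.82-0.87 against 0.66-0.78). All these inputs are assumed. This objection stands against changing the primary estimator.

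It is also fair that ranks bound an extreme score, and that MI or death takes the worst rank whatever the score. Bounding an outlier does not put the woman back at her proper rank, however.

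Finally, the pre-randomization case is narrow: a second film and a procedure outside the qualifying artery, all within four months. That limits its frequency. It does not defend including the segment, since the disclosed rationale of measuring progression on study does not reach change that finished before treatment began.

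**Conclusion.** The point holds in a limited form. As written, a segment outside the qualifying artery that is treated between entry film and randomization enters the primary score on pre-treatment change. With no minimum interval, it can dominate that score: 97% or more of the noise variance for any film within four months, given four segments with equal reading error.

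A reader might infer bias between arms. The documents do not support that for these films: they precede randomization, so they are balanced in expectation and cost noise and power only. Nor is the sample size wrong; it reproduces.

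No single power loss can be claimed. The protocol gives no reading SD, number of segments per woman, or rate and timing of procedures, and the simulated losses run from negligible to large depending on how many films are very early. The early weighting after randomization is a disclosed choice that merits a sensitivity analysis, not replacement.

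**What to change.** State in Section 10.2.1 that a segment whose concluding (pre-procedure) film precedes randomization is not an endpoint segment. Keep the mean of per-segment rates as the primary endpoint. Prespecify a sensitivity analysis in which each woman's score is the sum of MLD changes over her endpoint segments divided by the sum of their follow-up times, with the same rank test and the same rule for MI and death. That analysis shows how far early films after randomization, which the exclusion does not touch, drive the result.

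The cost is a sentence of wording, a date check in programming, and one more analysis. A few segments are lost. If the qualifying-artery criterion is applied up to randomization, a woman should keep at least her qualifying segment and so her score.
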